2.5 Correlative Studies Background

Given that response rates to PD-1 blockade in the advanced, platinum-refractory SCCHN setting approach 20%, there is strong interest in identifying biomarkers that predict clinical benefit. In a NSCLC population, PD-L1 expression in at least 50% of tumor cells yielded a response rate of 45.2%, compared with an objective response rate of 19.4% among all treated patients [53]. More recently, whole-exome sequencing of NSCLC tumors treated with PD-1 blockade revealed that higher mutational burden correlated with improved objective response rates [54]. Somatic alterations in tumor cells yield neoantigens which are thought to facilitate antigen-specific CD8+ T cell responses – suggesting that the genomic landscape of the tumor impacts PD-1 response. In SCCHN, stromal or tumor PD-L1 expression does appear to partially impact response, but even PD-L1 negative patients may respond to treatment – suggesting important mechanisms beyond PD-1:L1 interactions [42, 43]. Moreover, NK cell infiltration is thought to be increased among SCCHN tumors, and our own work has suggested that NK cell populations may be higher in immunologically rich SCCHN tumors [44, 49].

More recent work has sought to use more comprehensive immune-based metrics to characterize the tumor microenvironment. Cytometric profiling has identified immunologically ‘hot’ and ‘cold’ immunophenotypes which may identify tumors more likely to respond to immunotherapies [55, 56]. Studies confirming these findings in head and neck cancer patients are not yet published, although our own preliminary work has shown that a robust CD8+ T cell infiltrate and pattern of immune checkpoint co-expression may predict clinical benefit to PD-1 blockade in an advanced SCCHN population [57]. The window phase of treatment proposed in this study will allow evaluation of pre- and post-immunotherapy tumor samples, permitting investigation of immune microenvironment alterations to potentially identify mechanisms of response and resistance. Additionally, whether the circulating peripheral immune environment recapitulates the tumor immune microenvironment remains an unanswered question. By evaluating both the tumor and circulating immune profile, we hope to evaluate whether early

peripheral blood changes in immune parameters could parallel an early indication of treatment response, avoiding the cost and risk of sequential tumor biopsies. Understanding the genomic determinants which drive immunophenotype appear crucial and therefore whole exome and bulk RNA sequencing are also planned. Finally, we will attempt to correlate changes in tumor and lymph node radiologic measurements with immune microenvironment alterations and circulating immune parameters.

3. PARTICIPANT SELECTION

Participants must meet the following eligibility criteria on screening examination to be eligible to participate in the study:

3.1 Inclusion Criteria

- 3.1.1 Subject must have histologically or cytologically confirmed locoregionally recurrent squamous cell carcinoma of the head and neck (including any primary site, such as oral cavity, oropharynx, larynx or hypopharynx, and nasopharynx carcinoma)
 - 3.1.2 Must be a candidate for salvage surgery
 - 3.1.3 Willing to provide blood and tissue from diagnostic biopsy and at the time of surgery
 - 3.1.4 Has documented disease-free interval (DFI) > 8 weeks after completion of initial therapy; DFI is from the time of completion of initial treatment (from date last known disease-free at end of initial treatment) to the diagnosis of local or locoregional recurrence
 - 3.1.5 Any HPV status or smoking history is permitted. Oropharyngeal cancer patients are required to undergo HPV testing with p16 immunohistochemistry and/or confirmatory HPV PCR or ISH testing
 - 3.1.6 Age 18 years or older
 - 3.1.7 ECOG performance status ≤ 2 (Karnofsky $\geq 60\%$, see Appendix A)
 - 3.1.8 Participant must have normal organ and marrow function as defined below within 21 days prior to study registration:
 - leukocytes $\geq 3,000/\text{mcL}$
 - absolute neutrophil count $\geq 1,500/\text{mcL}$
 - platelets $\geq 100,000/\text{mcL}$
 - total bilirubin $\leq 2.0 \text{ g/dL}$
 - AST(SGOT)/ALT(SGPT) $\leq 2.5 \times$ institutional upper limit of normal
 - creatinine within normal institutional limits
- OR
- creatinine clearance $\geq 60 \text{ mL/min/1.73 m}^2$ (calculated using the Cockcroft-

Gault equation) for participants with creatinine levels above institutional normal

- 3.1.9 Ability to understand and the willingness to sign a written informed consent document
- 3.1.10 Women of childbearing potential (WOCBP) must agree to use appropriate method(s) of contraception. WOCBP should plan to use an adequate method to avoid pregnancy for 5 months (30 days plus the time required for nivolumab to undergo five half-lives) after the last dose of investigational drug
- 3.1.11 Women of childbearing potential must have a negative serum or urine pregnancy test (minimum sensitivity 25 iu/l or equivalent units of hcg) within 24 hours prior to the start of nivolumab

“Women of childbearing potential (WOCBP)” is defined as any female who has experienced menarche and who has not undergone surgical sterilization (hysterectomy or bilateral oophorectomy) or who is not postmenopausal. Menopause is defined clinically as 12 months of amenorrhea in a woman over 45 in the absence of other biological or physiological causes. In addition, to be defined as menopausal, women under the age of 55 must have a documented serum follicle stimulating hormone (FSH) level greater than 40 mIU/mL.

- 3.1.12 Men who are sexually active with WOCBP must agree to use any contraceptive method with a failure rate of less than 1% per year. Men who are sexually active with WOCBP will be instructed to adhere to contraception for a period of 7 months after the last dose of investigational product. Women who are not of childbearing potential (ie, who are postmenopausal or surgically sterile as well as azoospermic men) do not require contraception

See Appendix B for further guidance on contraception.

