6. DOSING DELAYS/DOSE MODIFICATIONS

There will be no dose reductions for nivolumab or lirilumab permitted. Doses of nivolumab or lirilumab may be interrupted, delayed, or discontinued depending on how well the participant tolerates the treatment. If a lirilumab dose is delayed beyond four weeks from the prior lirilumab dose, then subsequent lirilumab doses should be rescheduled, if needed, such that the patient receives both nivolumab and lirilumab at next visit

6.1 Administration both study drugs should be delayed for the following adverse events:

- Grade 2 non-skin, drug-related adverse event, with the exception of fatigue
- Grade 2 drug-related creatinine, AST, ALT and/or Total Bilirubin abnormalities
- Grade 3 skin, drug-related adverse event
- Grade 3 drug-related laboratory abnormality, with the following exceptions:
 - Grade 3 lymphopenia or asymptomatic amylase or lipase does not require dose delay
 - Grade \geq 3 AST, ALT, Total Bilirubin will require dose discontinuation

- Any adverse event, laboratory abnormality, or intercurrent illness which, in the judgment of the investigator, warrants delaying the dose of study medication.
Note: see Appendix C for guidelines on managing immune-related toxicities

Participants who require delay of nivolumab or lirilumab should be re-evaluated weekly or more frequently if clinically indicated and resume nivolumab or lirilumab dosing when re-treatment criteria (as described below) are met. Participants with a delay in dosing beyond 8 weeks should be considered for discontinuation of protocol treatment and discussed with the Overall PI.

Subsequent dosing may be re-started if subjects continue to meet laboratory criteria (baseline values). The investigator will determine if subsequent dosing is appropriate for subjects who have laboratory or clinical abnormalities that do not meet dose discontinuation criteria (described below). All related grade 2 toxicities should be discussed with the Overall PI, prior to subsequent dosing.

6.2 Administration of both study drugs should be permanently discontinued for the following adverse events:

- A grade 3 pneumonitis and grade 3 uveitis will require permanent discontinuation.
- Any grade 4 adverse event will require permanent discontinuation with the following exceptions:
 - Grade 4 electrolyte abnormalities that < 72 hours in duration
 - Grade 4 neutropenia < 5 days in duration

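### The bilirubin entry limit is printed in g/dL and so excludes nobody; separately, the creatinine-clearance limit carries a body-surface-area-indexed unit that its named formula does not return

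*Combined protocol and SAP*

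**What the plan says.** Section 3.1, criterion 3.1.8, opens with "Participant must have normal organ and marrow function as defined below within 21 days prior to study registration" and then lists numerical limits. Three matter here.

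- Bilirubin: "total bilirubin $\leq 2.0 \text{ g/dL".
- Transaminases: "AST(SGOT)/ALT(SGPT) $\leq 2.5 \times$ institutional upper limit of normal".
- Renal function: creatinine within institutional limits or, as an alternative, "creatinine clearance $\geq 60 \text{ mL/min/1.73 m}^2$ (calculated using the Cockcroft"-Gault equation). The alternative is offered only "for participants with creatinine levels above institutional normal".

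No other section gives a unit for bilirubin, a multiple of the upper limit of normal for it, or an instruction to index a Cockcroft-Gault result to BSA. Section 3.2.6 excludes patients with evidence of hepatitis B or C virus but sets no limit on liver function.

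Section 4.1 has an investigator confirm eligibility and the study team complete a checklist specific to the protocol. Section 13 restricts the primary efficacy population to eligible patients who have salvage surgery and start adjuvant treatment.

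Section 6 uses the same laboratory tests during treatment, but by grade. One trigger for delay is "Grade 2 drug-related creatinine, AST, ALT and/or Total Bilirubin abnormalities"; bilirubin of grade 3 or higher leads to discontinuation. The restart sentence reads "Subsequent dosing may be re-started if subjects continue to meet laboratory criteria (baseline values").

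**The concern.** An entry limit has to separate patients who may enter from those who may not. A bilirubin limit in grams per decilitre lies far outside the range of any patient's result, so it makes no such separation. A patient with raised bilirubin and AST/ALT within 2.5 times the upper limit meets the criteria as written. A site that screens sensibly must override the protocol text, and an auditor who reads the text literally would find no violation at any bilirubin value.

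The renal limit raises a different question. Its unit says that the value is standardised to 1.73 m²; its named formula gives a value that is not. A site must either disregard the unit or add a conversion that the protocol does not describe. The study is multi-institutional, so two sites could rule differently on the same patient.

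The main stake is the safety screen at entry. A secondary stake is consistency of the eligibility ruling, because eligibility is part of the definition of the primary efficacy population.

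**Working it through.** The plan has no calculated figure that rests on these limits, so there is none to reproduce. The check is one of units.

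**Bilirubin.** The input is the printed limit of 2.0 g/dL in criterion 3.1.8. Since 1 g/dL = 1,000 mg/dL, the limit is 2.0 × 1,000 = 2,000 mg/dL, which is 1,000 times the same number read in mg/dL. Illustrative results of 1.2, 2, 5, 10, 30 and 50 mg/dL are 0.0012, 0.002, 0.005, 0.01, 0.03 and 0.05 g/dL. All are below 2.0 g/dL and all pass.

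**Creatinine clearance.** The inputs from criterion 3.1.8 are the limit of 60 mL/min/1.73 m² and the Cockcroft-Gault equation. The formulas are:

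- Cockcroft-Gault (mL/min) = (140 − age) × weight in kg / (72 × creatinine in mg/dL), times 0.85 for women.
- BSA (m²) = √(height in cm × weight in kg / 3,600).
- Indexed clearance = Cockcroft-Gault × 1.73 / BSA.

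The unindexed value equivalent to the printed limit is 60 × BSA / 1.73. The BSA values below are assumptions.

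| BSA (m²) | Unindexed equivalent of 60 mL/min/1.73 m² |
|---|---|
| 1.4 | 48.6 mL/min |
| 1.5 | 52.0 mL/min |
| 1.73 | 60.0 mL/min |
| 2.0 | 69.4 mL/min |
| 2.2 | 76.3 mL/min |

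The two readings coincide for every clearance value only at 1.73 m².

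Two invented patients show that the disagreement runs both ways. Each is assumed to have a creatinine above the site's normal range, as the alternative requires.

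- Man, 65 years, 100 kg, 180 cm, creatinine 1.5 mg/dL. Cockcroft-Gault = 75 × 100 / (72 × 1.5) = 69.4 mL/min, which passes if 60 is read as mL/min. BSA = √(180 × 100 / 3,600) = 2.24. Indexed = 69.4 × 1.73 / 2.24, about 53.7 (BSA unrounded), which fails.
- Man, 40 years, 55 kg, 168 cm, creatinine 1.3 mg/dL. Cockcroft-Gault = 100 × 55 / (72 × 1.3) = 58.8 mL/min, which fails. BSA = √(168 × 55 / 3,600) = 1.60. Indexed = 58.8 × 1.73 / 1.60, about 63.5 (unrounded inputs), which passes.

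**Does the design depend on this?** Section 13 uses 37 events, a hazard ratio of 0.70 and one-sided 10% error. The null hazard is −ln(0.57) = 0.5621, and 0.70 times this is 0.3935, as stated. Power is Φ(√37 × |ln 0.70| − 1.2816) = Φ(0.888) = 81.3%, against the stated 81%. No laboratory limit enters this calculation.

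**The case against.** The strongest reply on bilirubin is that this is a one-letter slip which no site would apply literally. The criterion is introduced as a definition of normal organ function, and a limit of 2,000 mg/dL is absurd on its face. The AST/ALT limit and the hepatitis exclusions also screen for liver disease. The documents were converted from PDF by a program, so a lost letter cannot be ruled out, although other units in and around the criterion came through intact. The checklist that staff complete is not among the documents and may already carry a usable unit. All of this lowers the likely practical harm. It does not change what the operative text says, and no other passage supplies a unit to fall back on.

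On the renal limit, the reply is that the printed unit itself signals indexing, and that height and weight are recorded at screening (Section 10), so BSA can be computed. The limit also still excludes patients with clearly low clearance. This stands: the defect is an unstated step, and it would be wrong to say that the renal limit does not work. Its reach is narrow too, because the limit is only an alternative to normal creatinine. For example, a woman aged 75, 50 kg, 162 cm (BSA 1.5), with creatinine 0.70 mg/dL has a Cockcroft-Gault value of 65 × 50 / (72 × 0.70) × 0.85 = 54.8 mL/min. If 0.70 is within her institution's normal range, she qualifies through creatinine whichever way the clearance limit is read.

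A reader might also infer that the faulty limits carry into re-dosing. The documents do not support that. Section 6 handles bilirubin and creatinine by grade, does not mention creatinine clearance, and calls for related grade 2 toxicities to be discussed with the Overall PI before further dosing. Its restart sentence does not cite criterion 3.1.8, and its parenthesis about baseline can refer to the patient's own values.

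**Conclusion.** The point holds in two parts of unequal weight.

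The bilirubin limit, as printed, screens out no one at entry. It is 1,000 times the same number in mg/dL, and nothing elsewhere in the protocol repairs it. Because it is an operative safety threshold, it deserves correction even if most sites would read past it. The conclusion assumes that the source page also prints g/dL.

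The clearance limit is ambiguous. The ambiguity reaches only patients whose creatinine is above institutional normal, whose clearance is near 60 and whose BSA is away from 1.73 m². Over an assumed BSA range of 1.5 to 2.0 m², the two readings put the unindexed cut-off anywhere from 52.0 to 69.4 mL/min. The documents give no data from which to estimate how many patients this affects.

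It is tempting to go further and say that the primary analysis is compromised because its population is limited to eligible patients. The documents do not support that. Registration of 58 for an analysis of 54 leaves 58 − 54 = 4 places, which already allow for ineligibility along with other losses, and neither sample size nor power depends on these limits. What remains is an avoidable chance that an eligibility ruling turns on how a site read the unit.

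**What to change.** In criterion 3.1.8:

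1. Check the bilirubin unit against the source page and correct it. This is a unit correction only. Replacing the limit with a multiple of the upper limit of normal would change the threshold and is not requested.
2. State whether the Cockcroft-Gault result is used unindexed or indexed to BSA, so that unit and formula agree. If it is indexed, give the conversion and the BSA formula.
3. Bring the eligibility checklist into line with the corrected text.

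Which unit and which reading were intended is for the sponsor to say. Section 6 does not need to change on account of this point. The cost is a one-line edit for each limit plus a checklist update. No procedure is added, since height and weight are already collected at screening, and the statistical section is untouched.

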3.2 Exclusion Criteria

- 3.2.1 Existing significant autoimmune conditions. Patients with a history of Hashimoto thyroiditis who are stable on replacement hormone therapy are not excluded. Patients cannot be on long-term (> 4 weeks) corticosteroids at doses exceeding prednisone 20 mg (or its equivalent) prior to enrollment. Short-term corticosteroid dosing is permitted as long as steroids are discontinued within 2 weeks of study enrollment.
- 3.2.2 Subject who has had chemotherapy or radiotherapy within 4 weeks (6 weeks for nitrosoureas or mitomycin C) prior to entering the study or those who have not recovered from adverse events due to agents administered more than 4 weeks earlier.

- 3.2.3 Subject who has been treated with immunotherapy. This includes prior treatment with anti-PD-1, anti-PD-L1, anti-PD-L2, anti-CTLA-4 antibody, or any other antibody or drug specifically targeting T-cell co-stimulation or checkpoint pathways
- 3.2.4 Subject with known brain metastases should be excluded from this clinical trial because of their poor prognosis and because they often develop progressive neurologic dysfunction that would confound the evaluation of neurologic and other adverse events. However, baseline brain imaging is not required prior to enrollment in the study if patients are asymptomatic.
- 3.2.5 Uncontrolled intercurrent illness including, but not limited to, ongoing or active infection, symptomatic congestive heart failure, unstable angina pectoris, cardiac arrhythmia, or psychiatric illness/social situations that would limit compliance with study requirements.
- 3.2.6 Known human immunodeficiency virus carrier or a diagnosis of immunodeficiency. Any positive test result for hepatitis B virus or hepatitis C virus indicating presence of virus, eg, Hepatitis B surface antigen (HBsAg, Australia antigen) positive, or Hepatitis C antibody (anti-HCV) positive (except if HCV-RNA negative).
- 3.2.7 Known non-infectious pneumonitis or any history of interstitial lung disease.
- 3.2.8 Receipt of a live vaccine within 30 days of start of study treatment.

3.3 Inclusion of Women and Minorities

Both men and women of all races and ethnic groups are eligible for this study.

4. REGISTRATION PROCEDURES

4.1 General Guidelines for DF/HCC Institutions

An investigator will confirm eligibility criteria and a member of the study team will complete the protocol-specific eligibility checklist.

Eligible subjects will be registered by a member of the study team in the Clinical Trials Management System (CTMS) “OnCore”. Registrations must occur prior to the initiation of protocol therapy. Any subject not registered to the protocol before protocol therapy begins will be considered ineligible and registration will be denied.

Following registration, participants may begin protocol therapy. Issues that would cause treatment delays should be discussed with the Overall Principal Investigator (PI). If a participant does not receive protocol therapy following registration, the participant’s registration on the study must be canceled. Registration cancellations must be made in OnCore as soon as possible.

4.2 Registration Process for DF/HCC Institutions

DF/HCC Standard Operating Procedure for Human Subject Research Titled *Subject Protocol Registration* (SOP #: REGIST-101) must be followed.

4.3 General Guidelines for Other Investigative Sites

See DSMP appendix

4.4 Registration Process for Other Investigative Sites

See DSMP appendix

5. TREATMENT PLAN

Treatment will be administered on an outpatient basis. No investigational or commercial agents or therapies other than nivolumab (BMS-936558) and lirilumab (BMS-986015) may be administered with the intent to treat the participant's malignancy during the course of treatment.

5.1 Pre-Treatment Criteria

Eligibility and exclusion criteria are provided in Section 3. These criteria will be assessed 21 days prior to study registration to establish eligibility and baseline values.

Informed consent will be obtained after the study has been fully explained to the subject and before the conduct of any screening procedures or assessments.

Demographic information and baseline characteristics will be collected at the Screening Visit. Standard demographic parameters include age, sex, and race/ethnicity (recorded in accordance with prevailing regulations). Baseline characteristics will include ECOG PS (Appendix A), disease status, and medical histories.

5.2 Treatment Regimen

Patients will be premedicated with diphenhydramine, famotidine, and acetaminophen before lirilumab doses unless otherwise directed by treating investigator. Each treatment cycle will be 28 days long. On the days when both nivolumab and lirilumab are administered, nivolumab will be administered first, followed by lirilumab, with a 30-minute minimum duration time between the administration of nivolumab and lirilumab. Nivolumab infusion must be promptly followed by a saline flush to clear the line of nivolumab before starting the lirilumab infusion. Participants should be carefully monitored for infusion reactions during nivolumab and lirilumab administration. If an acute infusion reaction is noted, participants should be managed according to the algorithm described in Appendix C or in Nivolumab IB.

Nivolumab infusion time should be 30 (+/-10) minutes. A volumetric pump with a 0.2 - 0.22 micron in-line filter through an IV transfer set will be used.

Lirilumab infusion time should be 60 (+/-15) minutes. A volumetric pump with a 0.2 micron in-line filter through an IV transfer set will be used.

Window phase: Seven to twenty-one days prior to salvage surgical resection, a single dose of each study drug will be administered. Nivolumab 240 mg IV flat dosing will be administered through IV infusion, followed by lirilumab 240 mg IV flat dosing.

Salvage surgical resection: Each participant should be a candidate for salvage surgical resection to be able to participate in this study. Surgery should be performed no later than 4 weeks after study enrollment. Patients remain eligible to continue on study regardless of post-salvage surgery excisional margin status. Following salvage surgery, re-irradiation or additional chemotherapy is not permitted during the study period.

Adjuvant phase: Three to eight weeks after salvage surgery, treatment will restart. If additional surgery is required after the initial salvage surgery (e.g., for completion, reconstruction), treatment will restart after the additional surgery. In Cycle 1-3: Nivolumab will be administered on Days 1 and 15 and lirilumab will be administered on Day 1 of each 28 day long cycle. In Cycle 4-6 and beyond: Nivolumab and lirilumab will be administered on Day 1 of each 28 day long cycle. Treatment with both study drugs will continue for a maximum of 6 cycles or until disease progression or recurrence, unacceptable toxicity or withdrawal of consent. Nivolumab 240 mg IV flat dosing will be administered through IV infusion, followed by lirilumab 240 mg IV flat dosing.

5.2.1 Cycle 1, Day 1

If screening assessments occur within a week before start of study treatment, then they may serve as the baseline cycle 1 day 1 visit and cycle 1 day 1 labs do not need to be performed. Laboratory evaluations do not need to be repeated to meet eligibility criteria on cycle 1 day 1, if they were done within 3 days of the first treatment dose.

5.3 Pharmaceutical Properties and Formulation for Lirilumab:

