10. STUDY CALENDAR

Screening evaluations are to be conducted within 3 weeks prior to study registration. Procedures done within a week of study registration don't need to be repeated to establish baseline. Scans and x-rays must be done ≤ 4 weeks prior to the start of therapy. Laboratory evaluations do not need to be repeated to meet eligibility criteria on cycle 1 day 1, if they were done within 3 days of the first treatment dose. In an event that the participant's condition is deteriorating, laboratory evaluations should be repeated within 48 hours prior to initiation of the next cycle of therapy. Each treatment cycle in this study is 28 days long.

Assessments must be performed prior to administration of any study agent. Study assessments and agents should be administered within ± 3 days of the protocol-specified date, unless otherwise noted.

	Screening	Window Phase	Pre-surgery	Surgery	Adjuvant phase							End of Treatment	Follow up visit 30 days after last dose
					Cycle 1		Cycle 2		Cycle 3		Cycle 4-6		
					Day 1	Day 15	Day 1	Day 15	Day 1	Day 15	Day 1		
Informed consent	X												
Medical History	X												
Concomitant Medicines	X												
Physical exam (Ht, Wt, VS, PS) ^a	X	X			X	X	X	X	X	X	X	X	X
Routine labs ^b	X	X			X	X	X	X	X	X	X	X	X
FSH (if female <55 years old)	X												
HPV testing (oropharyngeal only)	X												
B-HCG (WOCBP only) ^c	X									X	X		
ECG	X									X	X		

Radiologic evaluation ^{d, g}	X		X	X								
Biopsy sample ^{e, f}	X										X ^h	
Correlative biopsy ^f	X										X ^h	
Correlative blood ⁱ	X ⁱ					X					X	
Nivolumab		X		X	X	X	X	X	X	X		
Lirilumab		X		X		X		X		X		
Adverse event evaluation		X		X	X	X	X	X	X	X	X	X

- a) Physical exam is symptom directed. Height measured at screening only.
- b) Routine labs include: CBC, LFTs, CMP, Mg, TSH, Free T4. Baseline HCV antibody, hepatitis B surface antigen, hepatitis B surface antibody, and hepatitis B core antibody testing is required. TSH and free T4 are required less frequently according to the following schedule: screening, window phase (D1 of pre-surgery immunotherapy dosing), D1 of each adjuvant cycle, and at the 30-day post protocol treatment visit.
- c) Serum or urine within 24 hours prior to first dose.

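### Section 5.2.1 ties its screening-lab waiver to Cycle 1 Day 1, the first adjuvant dose, although its terms fit only the window-phase dose; read literally, it waives the first scheduled post-exposure CBC, LFTs, CMP and Mg

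*Combined protocol and SAP*

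**What the plan says.** Section 5.2.1 is headed Cycle 1, Day 1 and follows directly after the adjuvant-phase paragraph of Section 5.2. Its first sentence sets a condition, "If screening assessments occur within a week before start of study treatment", and a consequence, "then they may serve as the baseline cycle 1 day 1 visit and cycle 1 day 1 labs do not need to be performed".

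The rest of the protocol places these events as follows.

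- **First dose (Section 5.2, window phase).** "Seven to twenty-one days prior to salvage surgical resection, a single dose of each study drug will be administered".
- **Adjuvant dosing (Section 5.2, adjuvant phase).** "Three to eight weeks after salvage surgery, treatment will restart". If further surgery is needed, "treatment will restart after the additional surgery". Cycles 1 to 6 are numbered from this point.
- **Order of screening, registration and treatment.** Section 10: "Screening evaluations are to be conducted within 3 weeks prior to study registration". Section 4.1: "Registrations must occur prior to the initiation of protocol therapy".
- **Calendar (Section 10).** Window Phase is a separate column, and the numbered cycles sit under the adjuvant heading. Routine labs are marked at Screening and Window Phase, left blank at Pre-surgery and Surgery, and marked again from Cycle 1 Day 1 onward. Footnote b defines them as CBC, LFTs, CMP, Mg, TSH and free T4, and gives the two thyroid tests their own schedule, which includes Day 1 of each adjuvant cycle.
- **Timing of assessments (Section 10).** "Assessments must be performed prior to administration of any study agent".

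**The concern.** The condition and the consequence of the waiver point to different visits. Screening, baseline and the start of study treatment all belong to the window-phase dose. Cycle 1 Day 1 belongs to the adjuvant restart, by which time the participant has received both drugs and had salvage surgery.

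The labs at stake support dosing decisions. Under Section 6.1, a grade 2 drug-related abnormality in creatinine, AST, ALT or total bilirubin delays both drugs, and grade 3 or higher AST, ALT or bilirubin requires discontinuation. A site that applied 5.2.1 as written could give the first adjuvant dose of both drugs with no scheduled post-exposure value for any of these. The case most likely to be missed is an abnormality in a participant who looks well, because the instruction in Section 10 to repeat labs within 48 hours before a cycle applies only when the participant is deteriorating.

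**Working it through.** The plan states no figure to reproduce. The check reads the calendar row against its columns and adds day ranges.

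**Inputs**

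| Interval | Days | Source |
|---|---|---|
| Screening to window dose, for the waiver to apply | 0 to 7 | 5.2.1 |
| Window dose to surgery | 7 to 21 | 5.2, window phase |
| Surgery to adjuvant Cycle 1 Day 1, no additional surgery | 21 to 56 | 5.2, adjuvant phase |
| Cycle 1 Day 1 to Cycle 1 Day 15 | 14 | 5.2, adjuvant phase |

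The 3-day visit tolerance in Section 10 is ignored except where stated.

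**Step 1. Which draw is the first after exposure?** The calendar has 13 columns. The routine-labs row has marks at Screening and Window Phase, blanks at Pre-surgery and Surgery, then nine marks from Cycle 1 Day 1 to the 30-day visit. The Window Phase labs precede the dose, because assessments come before any study agent. Cycle 1 Day 1 is therefore the first scheduled CBC, LFTs, CMP and Mg after exposure.

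**Step 2. Reading A: the start of study treatment is the window dose.**

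- Age of the screening labs at Cycle 1 Day 1 = (screening to window dose) + (window dose to surgery) + (surgery to Cycle 1 Day 1). Minimum 0 + 7 + 21 = 28 days; maximum 7 + 21 + 56 = 84 days. Additional surgery would lengthen this.
- First scheduled post-exposure draw under the calendar, at Cycle 1 Day 1: 7 + 21 = 28 to 21 + 56 = 77 days after the window dose, after one dose of each drug.
- First scheduled draw if the waiver is applied, at Cycle 1 Day 15: 28 + 14 = 42 to 77 + 14 = 91 days after the window dose, after two doses of each drug.
- Shift: 14 days and one further dose of each drug.

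This covers CBC, LFTs, CMP and Mg only. Footnote b separately fixes TSH and free T4 at Day 1 of each adjuvant cycle, so no thyroid delay is claimed.

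**Step 3. Reading B: the start of study treatment is the adjuvant restart.** Screening precedes registration, and registration precedes the window dose. The youngest possible screening labs at Cycle 1 Day 1 are then 0 + 7 + 21 = 28 days old, against an allowance of 7. Using the 3-day tolerance at both dosing visits gives (7 − 3) + (21 − 3) = 22 days, still more than 7. The waiver could never apply.

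**Step 4. Compare.** Reading A removes labs from a visit where the calendar requires them. Reading B leaves the sentence with no effect. The sentence works only if Cycle 1 Day 1 is replaced by the window-phase dose.

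**The case against.** The best reply is that the intended meaning is clear and a site would find it. The next sentence of 5.2.1, repeated in Section 10, ties Cycle 1 Day 1 to the first treatment dose when it excuses repeat eligibility labs. Section 10 also says that procedures done within a week of registration need not be repeated for baseline, which looks like the same anti-duplication rule. Section 11.1.1 uses cycle 1 loosely in its response-evaluability text. The harmful reading is a hybrid: it takes the window dose as the start of treatment but a visit 4 to 11 weeks later as baseline. The calendar still marks the labs, thyroid tests require a blood draw that day anyway, examination and adverse-event review are scheduled, and the Section 6.1 text on resuming after a delay refers to laboratory criteria.

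Most of this stands as evidence of intent: the window dose was almost certainly meant, and many sites would draw the labs regardless. It does not repair the rule. Nothing in the protocol defines the window dose as Cycle 1 Day 1, and footnote b lists the two separately. The calendar mark is what a specific waiver would be read as overriding, and the general rule on timing before dosing does not settle whether a waived assessment is due. Footnote b protects only the thyroid tests, and the Section 6.1 resumption text sits within the dose-delay rules. Peri-operative labs may be drawn as usual care, but the calendar schedules none.

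**Conclusion.** The concern holds. The first sentence of 5.2.1 is an operative rule attached to the wrong visit. Read literally, it allows pre-exposure labs 28 to 84 days old to replace the first scheduled post-exposure CBC, LFTs, CMP and Mg, and it moves that draw 14 days later, past the first adjuvant dose of both drugs. On the only other reading it has no effect.

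Confidence is high that the label is wrong. The safety consequence is a possible misapplication of permissive wording; the day ranges describe the literal reading and do not predict what sites would do. They assume the Section 5.2 intervals are kept and no additional surgery postpones the restart. The DFS analysis, power and sample size are unaffected. The eligibility-lab sentence in 5.2.1 and Section 10 carries the same label error but waives no safety labs.

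**What to change.** In the first sentence of 5.2.1, replace both mentions of Cycle 1 Day 1 with the window-phase dose, and change the subsection heading to match. Add one sentence stating that the routine labs scheduled at adjuvant Cycle 1 Day 1 are required before dosing. For consistency, correct the same visit label in the eligibility-lab sentence of 5.2.1 and in its repeat in Section 10.

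The cost is one wording amendment. The labs are already in the study calendar, so no visit, procedure or analysis is added.
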